Population: This study will include adult (≥ 18 years old) patients with an International Classification of Diseases, tenth revision (ICD-10) code for RRMM (defined as MM ICD-10 codes: C90.0x). The study cohort will include patients with RRMM who initiate elranatamab between 14 August 2023 (US approval date) and end of data (defined as the latest data available, at the time of the specified analysis). Exploratory analyses will also include a teclistamab-exposed cohort, which will include patients with RRMM who initiate teclistamab between 14 August 2023, and the end of data. The index date for patients in each cohort will be defined as the date of the first prescription or medical claim for elranatamab or teclistamab. Patients will be required to have at least 180 days of continuous closed-claims enrollment before the index date.

Variables: Variables used to define eligibility will include elranatamab, MM diagnosis, and observability.

Variables to define demographic and clinical characteristics will include, but are not limited to, age, sex, race/ethnicity, region, Charlson Comorbidity Index (CCI), and prior infections.

Prior treatment history will be captured based on the use of National Comprehensive Cancer Network (NCCN) guideline-recommended treatments, which include chimeric antigen receptor T cell therapy (CAR-T), PIs, and IMiDs.

HCRU and costs will be described overall and by place of service, including inpatient (IP) visits, outpatient visits (OP, defined as non-IP/non-ED), emergency department (ED) visits, and pharmacy claims. Additionally, HCRU and imputed costs will be reported as all-cause and MM-related.

Adverse events (AEs) will include cytokine release syndrome (CRS), immune effector cell-associated neurotoxicity syndrome (ICANS), peripheral neuropathy, and infections. Effectiveness outcomes will include TTNT/D and OS.

Country of Study: US

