2.0	31 July 2025	Administrative	ANNEX	Inclusion of the most update to date ANNEX containing study variables. Multiple Myeloma codes were added into the Any Malignancy component for the CCI score.	Data was received from the vendor containing information on laboratory test results and patterns. MM codes were added into the CCI

					definition to accurately reflect the published definition of CCI.
--	--	--	--	--	---

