9.2. Setting

This study will evaluate adult patients with RRMM who initiate elranatamab. Patients will enter (i.e., index) on the first observed elranatamab claim between 14 August 2023 and the end of data (defined as the latest data at the time of the specified analysis). Limited eligibility criteria will be applied.

Study Period: Start of data availability (01 January 2016) to the end of data

MM diagnosis window: Start of data availability (01 January 2016) to index date

Index date: First elranatamab claim after initial MM diagnosis

Observability: At least 180 days of continuous closed-claims medical and pharmacy enrollment prior to index (inclusive)

[figure not shown]
Baseline period for MM-related treatments and MM-related comorbidities: MM diagnosis to one day prior to index date (unless otherwise specified)

CCI and baseline HCRU assessment window: 180 days prior to index date to index date.

Follow-up: Index date until death, the earliest of the end of data, or end of continuous enrollment (unless otherwise noted). Alternative censoring criteria will be applied for certain outcomes (such as OS, TTD, and TTNT/D); see [Section 9.7](#) for more details.

Figure 1 reflects the time periods of interest in the study cohort.

Figure 1. Study Schematic for Patients Receiving Elranatamab

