9.2.1. Inclusion Criteria

Patients must meet all of the following inclusion criteria to be eligible for inclusion in the study:

1. Index date: First observed prescription claim or medical claim for elranatamab in the dataset (14 August 2023 to the end of data)
2. Age 18 or older on index date

3. Diagnosis of RRMM (defined as MM) any time prior to index date
4. At least 180 days of continuous closed-claims medical and pharmacy enrollment prior to index (inclusive)

For the exploratory cohort of patients receiving teclistamab, patients will be required to meet the same inclusion criteria as those receiving elranatamab. The only difference is that patients will index on their first teclistamab claim within the same time window (14 August 2023 to the end of data).

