1	Neutropenia	Medical claim with an ICD-10 code in the IP or non-IP setting for neutropenia (dichotomous) or event in the lab table where absolute neutrophil count is < 1,500 cells per μ L	MM diagnosis to 1 day prior to index date
1	Hypercalcemia	Medical claim with an ICD-10 code in the IP or non-IP setting for hypercalcemia (dichotomous) or an event in the lab table where corrected serum calcium is > 11.5 mg/dL	MM diagnosis to 1 day prior to index date
1	Hepatotoxicity	Medical claim with an ICD-10 code in the IP or non-IP setting for hepatotoxicity (dichotomous)	MM diagnosis to 1 day prior to index date

Objective	Variable	Definition	Assessment Period(s)
1	Renal failure	Medical claim with an ICD-10 code in the IP or non-IP setting for renal failure (dichotomous)	MM diagnosis to 1 day prior to index date
1	Amyloidosis	Medical claim with an ICD-10 code in the IP or non-IP setting for amyloidosis (dichotomous)	MM diagnosis to 1 day prior to index date
1	Hypertension	Medical claim with an ICD-10 code in the IP or non-IP setting for hypertension (dichotomous)	MM diagnosis to 1 day prior to index date
1	Extramedullary disease	Medical claim with an ICD-10 code in the IP or non-IP setting for extramedullary disease (dichotomous)	MM diagnosis to 1 day prior to index date
1	CCI score	CCI ¹⁷ (continuous and categorical): 0 (no comorbidities) 1 to 2 (mild) 3 to 4 (moderate) ≥ 5 (severe)	180 days prior to index date to index date
1	Myocardial infarction	Medical claim with an ICD-10 code in the IP or non-IP setting for myocardial infarction (dichotomous)	180 days prior to index date to index date
1	Congestive heart failure	Medical claim with an ICD-10 code in the IP or non-IP setting for congestive heart failure (dichotomous)	180 days prior to index date to index date
1	Peripheral vascular disease	Medical claim with an ICD-10 code in the IP or non-IP setting for peripheral vascular disease (dichotomous)	180 days prior to index date to index date
1	Cerebrovascular disease	Medical claim with an ICD-10 code in the IP or non-IP setting for cerebrovascular disease (dichotomous)	180 days prior to index date to index date

Objective	Variable	Definition	Assessment Period(s)
1	Dementia	Medical claim with an ICD-10 code in the IP or non-IP setting for dementia (dichotomous)	180 days prior to index date to index date

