Diabetes with chronic complications	Baseline characteristic - Clinical	Claims data	ICD-10 Diagnosis: E08.2x, E08.3x, E08.4x, E08.5x, E09.2x, E09.3x, E09.4x, E09.5x, E10.2x, E10.3x, E10.4x, E10.5x, E11.2x, E11.3x, E11.4x, E11.5x, E13.2x, E13.3x, E13.4x, E13.5x	Glasheen et al. (2019)

PFIZER CONFIDENTIAL

Redacted

Mild or moderate renal disease	Baseline characteristic - Clinical	Claims data	ICD-10 Diagnosis: I12.9, I13.0, I13.10, N03.x, N05.x, N18.1, N18.2, N18.3, N18.4, N18.9, Z94.0	Glasheen et al. (2019)
Severe renal disease	Baseline characteristic - Clinical	Claims data	ICD-10 Diagnosis: I12.0, I13.11, I13.2, N18.5, N18.6, N19.x, N25.0, Z49.x, Z99.2	Glasheen et al. (2019)
Hemiplegia or paraplegia	Baseline characteristic - Clinical	Claims data	ICD-10 Diagnosis: G04.1, G11.4, G80.0, G80.1, G80.2, G81.x, G82.x, G83.x	Glasheen et al. (2019)
Human immunodeficiency virus	Baseline characteristic - Clinical	Claims data	ICD-10 Diagnosis: B20.x	Glasheen et al. (2019)
Metastatic solid tumor	Baseline characteristic - Clinical	Claims data	ICD-10 Diagnosis: C77.x, C78.x, C79.x, C80.0, C80.2	Glasheen et al. (2019)
Any malignancy	Baseline characteristic - Clinical	Claims data	ICD-10 Diagnosis: C0x.x, C1x.x, C2x.x, C30.x, C31.x, C32.x, C33.x, C34.x, C37.x, C38.x, C39.x, C40.x, C41.x, C43.x, C45.x, C46.x, C47.x, C48.x, C47.x, C48.x, C49.x, C50.x, C51-C58.x, C60-C63.x, C76.x, C80.1, C81.x, C82.x, C83.x, C84.x, C85.x, C88.x, C9x.x	Glasheen et al. (2019)
Albumin serum	Baseline characteristic - Lab	Claims data	An event in the lab results table where the result_abbrev is albumin serum and result_units are g per dL	
ALT	Baseline characteristic - Lab	Claims data	An event in the lab results table where the result_abbrev is ALT and result_units are IU per L	
AST	Baseline characteristic - Lab	Claims data	An event in the lab results table where the result_abbrev is AST and result_units are IU per L	
Neutrophil count	Baseline characteristic - Lab	Claims data	An event in the lab results table where the result_abbrev is neutrophils count and result_units are thousand per μ L	

PFIZER CONFIDENTIAL

Redacted

Creatinine	Baseline characteristic - Lab	Claims data	An event in the lab results table where the result_abbrev is creatinine serum and result_units are mg per dL	
Hemoglobin	Baseline characteristic - Lab	Claims data	An event in the lab results table where the result_abbrev is hemoglobin and result_units are g per dL	

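### The CCI scores multiple myeloma, the inclusion diagnosis, but the Table 2 bands are labelled as if it did not count

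*Protocol*

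**What the plan says.** **Eligibility.** Protocol section 9.2.1 requires "Diagnosis of RRMM (defined as MM) any time prior to index date". The Abstract gives the code set: "code for RRMM (defined as MM ICD-10 codes: C90.0x").

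**Score.** The current Annex 2 row for any malignancy, one of the CCI components, ends "C81.x, C82.x, C83.x, C84.x, C85.x, C88.x, C9x.x" and makes no exception for C90.0x. This is intended. The section 5 log records that "Multiple Myeloma codes were added into the Any Malignancy component for the CCI score", the reason given being agreement with the published index, and the Annex now matches that entry.

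**Windows.** Section 9.2 states "CCI and baseline HCRU assessment window: 180 days prior to index date to index date", and separately "MM diagnosis window: Start of data availability (01 January 2016) to index date".

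**Bands.** Table 2 in section 9.3 reports the CCI both as a continuous variable and in categories labelled "0 (no comorbidities) 1 to 2 (mild) 3 to 4 (moderate"), with 5 or more called severe.

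**The concern.** The disease that defines the cohort is counted as a comorbidity, while the category labels describe a score in which it is not. The lowest label says the patient has no comorbidity, yet a patient whose only disease is MM does not land there if that disease was coded in the window.

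Describing clinical history is part of primary Objective 1, and the CCI is its summary comorbidity score. A baseline table with few patients in the lowest band and raised categories above it would invite readers to see a more comorbid cohort than the non-MM conditions support. Section 9.9 already warns that early recipients may have more severe or advanced disease, so the raised bands could be mistaken for confirmation.

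The protocol keeps MM apart elsewhere: the Annex 2 row for other hematological malignancies excludes C90.0x. The CCI bands did not get the same treatment.

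**Working it through.** The protocol states no CCI distribution, so there is no planned figure to reproduce. The check is one of code overlap and band mapping.

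**Inputs from the protocol**
- Eligibility codes: C90.0x (Abstract; Annex 2).
- CCI malignancy codes: include C9x.x without exclusion (Annex 2).
- CCI window: 180 days before index up to index (section 9.2; Table 2).
- Bands: 0, 1-2, 3-4, 5 or more (Table 2).

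**Input not in the protocol**
- Weight *w* of the malignancy component. Annex 2 only refers to the components. It is assumed to be positive, and *w* = 1 and *w* = 2 are shown.

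**Step 1: overlap.** C90.00, C90.01 and C90.02 each fit the eligibility pattern C90.0x and the CCI pattern C9x.x. Any MM claim inside the window therefore triggers the malignancy component.

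**Step 2: score.** Let *s* be the score from all conditions other than MM. For a patient with an MM claim in the window and no other code in that component:

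CCI = *s* + *w*

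With *w* > 0, CCI > 0 even when *s* = 0. For a patient who already has another malignancy in the same component, MM adds nothing, provided the component is scored once.

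**Step 3: bands.** The column *w* = 0 is the score without MM, which is what the labels describe.

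| *s* | *w* = 0 | *w* = 1 | *w* = 2 |
|---|---|---|---|
| 0 | none | mild (1) | mild (2) |
| 1 | mild | mild (2) | moderate (3) |
| 2 | mild | moderate (3) | moderate (4) |
| 3 | moderate | moderate (4) | severe (5) |
| 4 | moderate | severe (5) | severe (6) |
| 5 or more | severe | severe | severe |

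At both weights the first row leaves the zero band. The severe band can only gain patients. The moderate band gains from below and loses to severe: at *w* = 1 it gains *s* = 2 and loses *s* = 4; at *w* = 2 it gains *s* = 1-2 and loses *s* = 3-4. Its net change depends on the distribution of *s*, which is not given.

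**Step 4: who can still score 0.** The MM diagnosis may date from any time since January 2016, whereas the CCI looks back 180 days. Section 9.2.1 also lets a patient index on a prescription claim. A patient whose C90.0x claims all precede the window, and who indexes on such a claim, can score 0 if nothing else is coded. That zero arises because no MM claim fell in the window, although the patient is starting an MM drug.

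**The case against.** The strongest reply is that the scoring is deliberate. The sponsor added the MM codes to follow the published index, and whether to count the index disease in a cancer cohort's CCI is a reporting choice. That stands for the score. It does not repair the labels, because the lowest one remains untrue for a patient with MM and no other condition.

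Second, little depends on the variable. The CCI is not an eligibility criterion, no formal comparison between groups is planned (section 9.7), and the Kaplan-Meier analyses of infection onset, overall survival and time to next treatment or death are stated to be unadjusted. Most component conditions have their own rows in Table 2, and the continuous CCI is shown beside the bands. All of this stands and limits the importance of the point.

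Third, table shells are listed in Annex 1 and might carry a footnote. They are dated 23 May 2024, before the 31 July 2025 protocol version, and are not shown, so this cannot be settled. The bands and labels are fixed in the protocol itself.

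A reader might also infer more than the documents support:
- *That the zero band must be empty.* It stays reachable, as Step 4 shows. That nearly every patient has an MM claim in the window is plausible, but no figure supports it.
- *That everyone moves up by 2 points.* No weight is printed. At weight 1, MM plus one point stays mild and MM plus three points stays moderate.
- *That the moderate band is inflated.* Its net change is undetermined.
- *That outcomes are biased.* No planned estimate is stated to use the CCI.

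**Conclusion.** The point holds as a labelling fault in the categorical CCI. Any patient with an MM claim in the window scores above 0 because of the inclusion diagnosis, and one with no other scoring condition is reported as at least mildly comorbid. This conclusion needs only a positive malignancy weight.

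The size of the shift rests on the assumed weight (1 or 2 shown). Its direction does not: for patients without another coded malignancy the band stays the same or rises. The number of patients affected cannot be derived from the protocol.

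The reach is narrow: one descriptive baseline variable, in both the elranatamab and teclistamab cohorts. It merits correction because it belongs to a primary objective and is cheap to put right.

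**What to change.** Derive a second CCI with C90.0x left out of the malignancy component, and apply the existing bands (0, 1-2, 3-4, 5 or more) to it. Keep the published CCI, including MM, as the continuous score, with a footnote that MM sets its floor for patients with an MM claim in the window. Print the component weights in Annex 2 so that readers can relate the two scores.

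The derivation uses codes already pulled and needs no new data. The cost is one extra derived variable, one table row and a footnote; the drawback is two CCI versions in the same table. If only one version is wanted, the lighter alternative is to re-base and relabel the bands so that the lowest means no comorbidity other than MM. In the section 6 milestones, refreshes 3 and 4 and the final report are all dated after the current protocol version.

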1	Neutrophil count	Lab event with neutrophil as the test name and thousands/ μ L as the result units (dichotomous)	180 days prior to index date to index date
		Most recent numeric value to index date of a lab event with neutrophil count as the test name and thousands/ μ L result units (continuous)	
1	Creatinine	Lab event with creatinine as the test name and mg/dL as the result units (dichotomous)	180 days prior to index date to index date

Objective	Variable	Definition	Assessment Period(s)
		Most recent numeric value of a lab event to index date with creatinine as the test name and mg/dL as the result units (continuous)	
1	Hemoglobin	Lab event with hemoglobin as the test name and g/dL as the result units (dichotomous)	180 days prior to index date to index date
		Most recent numeric value of a lab event with hemoglobin as the test name and g/dL as the result units (continuous)	
1	Lymphocyte count	Lab event with lymphocyte count as the test name and thousand/ μ L as the result units (dichotomous)	180 days prior to index date to index date
		Most recent numeric value of a lab event with lymphocyte count as the test name and thousand/ μ L as the result units (continuous)	
1	Monocyte count	Lab event with monocyte count as the test name and thousand/ μ L as the result units (dichotomous)	180 days prior to index date to index date
		Most recent numeric value of a lab event with monocyte count as the test name and thousand/ μ L as the result units (continuous)	
1	Platelet Count	Lab event with platelet count as the test name and thousand/ μ L as the result units (dichotomous)	180 days prior to index date to index date
		Most recent numeric value of a lab event with platelet count as the test name and thousand/ μ L as the result units (continuous)	

Objective	Variable	Definition	Assessment Period(s)
1	Serum immunoglobulin A (IgA)	Lab event with IGA as the test name and mg/dL as the result units (dichotomous)	180 days prior to index date to index date
		Most recent numeric value of a lab event with IGA as the test name and mg/dL as the result units (continuous)	
1	Serum immunoglobulin G (IgG)	Lab event with IGG as the test name and mg/dL as the result units (dichotomous)	180 days prior to index date to index date
		Most recent numeric value of a lab event with IGG as the test name and mg/dL as the result units (continuous)	

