1	Serum immunoglobulin E (IgE)	Lab event with IGE as the test name and IU/mL as the result units (dichotomous)	180 days prior to index date to index date
		Most recent numeric value of a lab event with IGE as the test name and IU/mL as the result units (continuous)	
1	Serum immunoglobulin M (IgM)	Lab event with IGM as the test name and mg/dL as the result units (dichotomous)	180 days prior to index date to index date
		Most recent numeric value of a lab event with IGM as the test name and mg/dL as the result units (continuous)	
1	Bone marrow plasma cell percent	Lab event with bone marrow plasma cell percent as the test name and percent as the result units (dichotomous)	Most recent value recorded in the 180 days prior to index date to index date
		Most recent numeric value of a lab event with bone marrow plasma cell	

Objective	Variable	Definition	Assessment Period(s)
		percent as the test name and percent as the result units (continuous)	
1	M-Protein	Lab event with M-Spike as the test name and as the g/dL as the result units (dichotomous)	180 days prior to index date to index date
		Most recent numeric value of a lab event with M-Spike as the test name and g/dL as the result units (continuous)	

1. Variable assessed both at baseline and in follow-up

Table 3 includes definitions and assessment periods for all study variables being used as outcomes. The full code list can be found in ANNEX 2. ADDITIONAL INFORMATION. If applicable, the frequency and percentage of patients with missing data for each variable will be described.

Table 3. Key Variables of Interest

Objective	Variable	Definition	Assessment Period(s)
Treatment exposure			
2	Use of premedication	
Medical or pharmacy claim with evidence of an NDC, HCPCS, generic name or CPT code for the following premedications (dichotomous):
 
Acetaminophen
 
Dexamethasone
 
Diphenhydramine
	
Step-Up Dosing Period
 
See Section 9.7.2 for censoring criteria

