Exploratory Obj 1	ICANS ¹	Medical claim with an ICD-10 code in the IP, non-IP or pharmacy setting for CRS, categorized into the following grades (categorical): Any (all grades and unspecified grade) Grade 1 Grade 2 Grade 3 Grade 4 Grade 5 If patients have multiple, conflicting grades, then the highest recorded grade will be reported	Index date to end of follow-up, where follow-up will be based on last dose of elranatamab (eg, 14 days after last recorded dose or 90 days after last recorded dose). See Section 9.7.6 for censoring criteria
Hematologic events			
Exploratory Obj 1	Anemia ¹	Medical claim with an ICD-10 code in the IP, non-IP, or pharmacy setting for anemia or event in the lab table where hemoglobin is <10g/dL (dichotomous)	Index date to end of follow-up, where follow-up will be based on last dose of elranatamab (eg, 14 days after last recorded dose or 90 days after last recorded dose). See Section 9.7.6 for censoring criteria

Exploratory Obj 1	Neutropenia ¹	Medical claim with an ICD-10 code in the IP, non-IP, or pharmacy setting for lymphopenia or event in the lab table where lymphocyte count is < 1,000 per uL (dichotomous)	Index date to end of follow-up, where follow-up will be based on last dose of elranatamab (eg, 14 days after last recorded dose or 90 days after last recorded dose). See Section 9.7.6 for censoring criteria
Exploratory Obj 1	Lymphopenia ¹	Medical claim with an ICD-10 code in the IP, non-IP, or pharmacy setting for lymphopenia or event in the lab table where lymphocyte count is < 1,000 per uL (dichotomous)	Index date to end of follow-up, where follow-up will be based on last dose of elranatamab (eg, 14 days after last recorded dose or 90 days after last recorded dose). See Section 9.7.6 for censoring criteria
Non-hematologic events			
Exploratory Obj 1	Hypogammaglobulinemia ¹	Medical claim with an ICD-10 code in the IP, non-IP, or pharmacy setting for hypogammaglobulinemia or event in the lab table where IGG value is ≤ 400 mg/dL (dichotomous)	Index date to end of follow-up, where follow-up will be based on last dose of elranatamab (eg, 14 days after last recorded dose or 90 days after last recorded dose). See Section 9.7.6 for censoring criteria

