9.7.1. Descriptive Analysis

Dichotomous and categorical variables will be summarized by the number and percentage of patients in each category. Continuous variables will be described using mean (SD), median (IQR), minimum, and maximum. If applicable, the frequency and percentage of patients with missing data for each variable will be described. Furthermore, baseline characteristics will be assessed among elranatamab or teclistamab patients with and without a laboratory observation.

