Lymphocyte count	Baseline characteristic - Lab	Claims data	An event in the lab results table where the result_abbrev is lymphocytes count and result_units are thousand per µL	
Monocyte count	Baseline characteristic - Lab	Claims data	An event in the lab results table where the result_abbrev is monocytes count and result_units are thousand per µL	
Platelet Count	Baseline characteristic - Lab	Claims data	An event in the lab results table where the result_abbrev is platelets and result_units are thousand per µL	
ImmunoglobulinA	Baseline characteristic - Lab	Claims data	An event in the lab results table where the result_abbrev is IGA and result_units are mg per dL	
ImmunoglobulinG	Baseline characteristic - Lab	Claims data	An event in the lab results table where the result_abbrev is IGG and result_units are mg per dL	
ImmunoglobulinE	Baseline characteristic - Lab	Claims data	An event in the lab results table where the result_abbrev is IGE and result_units are IU per mL	
ImmunoglobulinM	Baseline characteristic - Lab	Claims data	An event in the lab results table where the result_abbrev is IGM and result_units are mg per dL	
Bone marrow plasma cell percent	Baseline characteristic - Lab	Claims data	An event in the GDD table where the test is bone_marrow and result_units are percent	
M-Protein	Baseline characteristic - Lab	Claims data	An event in the GDD table where the test is m-spike and result_units are mg/dL	
Use of premedication	Outcome - Dosing and Administration Patterns	Claims data	HCPSCS (Mapped via SEER [Dexamethasone only] or Athena – OHDSI using generic name): J0136, J0137, J0134, J0131, C9283, G6039, J1200, Q0163, J8540, J1100, J1094	SEER (2024) ELREXFIO Label

PFIZER CONFIDENTIAL

Redacted

			Generic names (and associated NDCs): Acetaminophen, Dexamethasone, Diphenhydramine	
Inpatient	Baseline characteristic, Outcome - HCRU	Claims data	Any event in the inpatient table or an event in the non-inpatient table where acute_subacute is “acute inpatient” or where utilization type is “professional services” and service subcategory contains the term “hospital/ip encounter”	
OP	Baseline characteristic, Outcome - HCRU	Claims data	Any event in the non-inpatient table where utilization type is outpatient and service subcategory is not “emergency dept encounter”	
ED	Baseline characteristic, Outcome - HCRU	Claims data	Any event in the non-inpatient table where utilization type is “outpatient” and service subcategory is “emergency dept encounter”	

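### Table 2 admits only numeric results for continuous baseline labs; if below-limit results are stored as text, immunoglobulin and M-protein summaries are biased upward

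*Protocol*

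**What the plan says.** Table 2 gives two items for each laboratory test. For IgA, the yes/no item is "Lab event with IGA as the test name and mg/dL as the result units (dichotomous", with no condition on the form of the result. The continuous item is "Most recent numeric value of a lab event with IGA as the test name and mg/dL as the result units (continuous". IgG, IgE and IgM follow the same pattern, and the M-protein item is "Most recent numeric value of a lab event with M-Spike as the test name and g/dL as the result units (continuous". The assessment window for these rows is "180 days prior to index date to index date".

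Section 9.7.1 fixes the summaries: "Continuous variables will be described using mean (SD), median (IQR), minimum, and maximum". Where relevant, it has missing values counted for each variable. It also plans a split of baseline characteristics by whether the patient has a laboratory observation. Neither Table 2, Section 9.7.1 nor Annex 2 says what happens to a result reported as below or above an assay limit. Section 9.8 commits the analysts to following the protocol strictly.

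In Table 3, the laboratory arm of hypogammaglobulinemia is "event in the lab table where IGG value is ≤ 400 mg/dL (dichotomous", alongside an ICD-10 arm.

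**The concern.** The word 'numeric' in the continuous item works as a filter. A result reported as `<x` or 'not detected' carries information, because it places the patient at the bottom of the distribution. The rule makes such a result ineligible if it is held as text. What remains is an older measurable value or nothing, so the exclusion depends on the value itself.

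Section 7 says that antibody production is impaired in multiple myeloma, so low immunoglobulins are to be expected in this cohort. The laboratory rows were added in version 2.0 as Objective 1 characteristics. If the low end is removed, the cohort looks less immunosuppressed than it is, and M-protein is summarised only among patients with a measurable amount.

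**Working it through.** **What follows from the wording.** Suppose a patient's latest IgA is held as `<x`.

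- Yes/no item: the event counts if test name and units match.
- Continuous item: the result is not numeric, so it is skipped. An earlier numeric result within the window is used if there is one; otherwise the value is missing.
- With one common assay limit, any replacing value is at or above that limit, so the substitution can only raise the value.
- For a latest result held as `>x`, the same logic lowers the value.

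**Size.** The protocol has no figure to reproduce: it gives no laboratory distribution, assay limit or below-limit share. All inputs here are assumptions:

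- latest value lognormal, with log-SD σ = 0.7 or 1.2;
- one older value in the window, correlated 0.6 or 0.9 with the latest on the log scale;
- one common assay limit;
- a share p = 0, 5, 20 or 40% of latest results below the limit and held as text.

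If those results simply become missing, the reported median is the (1+p)/2 quantile of the true distribution, so the factor is exp(σ · z at (1+p)/2):

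- p = 5%: z at 0.525 = 0.0627; exp(0.7 × 0.0627) = 1.04 and exp(1.2 × 0.0627) = 1.08
- p = 20%: z at 0.60 = 0.2533; 1.19 and 1.36
- p = 40%: z at 0.70 = 0.5244; 1.44 and 1.88

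A simulation of 400,000 patients per scenario agrees and adds the case where an older numeric value is substituted when available. Ratios to the true latest values, as ranges over σ and the correlation:

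| Below limit, as text | Median, dropped | Median, replaced | Mean, dropped | Mean, replaced |
|---|---|---|---|---|
| 0% | 1.00 | 1.00 | 1.00 | 1.00 |
| 5% | 1.04–1.08 | 1.02–1.05 | 1.04–1.05 | 1.02–1.03 |
| 20% | 1.19–1.36 | 1.14–1.26 | 1.17–1.22 | 1.13–1.17 |
| 40% | 1.44–1.88 | 1.36–1.72 | 1.38–1.55 | 1.32–1.44 |

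**Would the planned tables show it?** Only in part. At p = 20% with replacement, 10% of patients end with no value at correlation 0.6 and 15% at 0.9. The other 20 − 10 = 10% or 20 − 15 = 5% carry an older, higher value and appear as ordinary observations. A missing count shows the first group without its reason and cannot show the second.

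**After the change.** If below-limit results stay as the latest result and are ranked at the bottom, the median is unchanged as long as fewer than half are below the limit. The ratio is then 1.00 at every share above. At 40% the lower quartile would be reported as below the limit, since 40% exceeds 25%.

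**The case against.** The strongest reply is that the premise is not in the documents. They do not say that below-limit text entries exist in the laboratory or GDD tables, how they are stored, or how common they are. If the vendor stores the limit or zero in a numeric field, nothing is skipped. This stands, and it is why the point is conditional. A reader might infer from the wording that low results are in fact being discarded and levels are in fact overstated; the documents do not support that.

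Nor is the net direction settled. Section 7 also describes a rise in M-protein, so high values are expected too, and `>x` results held as text would pull the other way. For an involved immunoglobulin the net effect could go either way.

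It can also be said that parsing of laboratory text belongs in an analysis plan or programming specification that is not shown. That would answer a protocol that was silent. Here the protocol states the rule, and a later document that kept censored results would depart from it.

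A reader might further infer that severe hypogammaglobulinemia is under-counted. This is weaker. The Table 3 criterion does not contain the word 'numeric', a result of `<200` meets a threshold of at most 400 in plain meaning, and Annex 2 gives an ICD-10 route (D80.1, D80.3). The wording merely leaves room for a program to miss such a result.

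Finally, the consequence is bounded. These are baseline descriptors; no eligibility criterion uses them and no formal comparison between groups is planned. A gap between the yes/no count and the continuous n would reveal dropped patients, though not replaced values.

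**Conclusion.** The point holds in conditional form. Table 2 states a rule that passes over a non-numeric latest result, and nothing in the protocol says how a censored result is to be kept. If below-limit results are stored as text, their effect on immunoglobulin and M-protein summaries is upward. Across the assumed scenarios the median factor runs from 1.00 (no text results) through 1.02–1.08 (5%) and 1.14–1.36 (20%) to 1.36–1.88 (40%). These figures rest on an assumed lognormal shape, one assay limit and assumed shares; they show scale and do not estimate what this database would give. The change is worth making because it is cheap and leaves results as they are if no text results exist. It does not threaten the study's main conclusions.

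**What to change.** In Table 2 and Section 9.7.1:

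1. Define the continuous value as the most recent result in the window, whether numeric or censored.
2. Report the number and percent of patients whose result is below (or above) the limit, separately from those with no result.
3. For the median and IQR, rank below-limit results lowest and above-limit results highest; show a quartile that falls in the censored range as below or above the limit.
4. Report mean and SD only when few results are censored.
5. If limits differ between laboratories, say how they are put on a common footing, because simple ranking assumes one limit.

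For the IgG criterion in Table 3, state that `<x` counts as meeting it when x is at or below the protocol's own 400 mg/dL.

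The cost is a text-parsing step and a few sentences; some tests may have no reported mean. Before coding, check how the vendor stores these results.

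A separate matter in the same M-protein row should be settled in the same edit: Table 2 requires g/dL, while Annex 2 reads "An event in the GDD table where the test is m-spike and result_units are mg/dL". The units differ by a factor of 1000 (1 g = 1000 mg) and must be reconciled.
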